### Study Design

This is a Phase 1, multicenter, open-label, dose-escalation study in subjects with PAD and DFU. The study will enroll up to 24 subjects. The study will utilize a 3 + 3 dose escalation design with 3 to 6 subjects enrolled into each of 4 dose cohorts ( $3 \times 10^6$  cells,  $10 \times 10^6$  cells,  $30 \times 10^6$  cells, and  $100 \times 10^6$  cells). Initially, 3 subjects will be enrolled to receive  $3 \times 10^6$  cells on Study Days 1 and 8. Progression to higher (or lower) PDA-002 dose levels will be based on the criteria found in [Table 1](#) of Section 4.1, Study Design.

All subjects in a given dosing-cohort must complete 14 days of follow-up and the data must be reviewed by the sponsor's internal Data Monitoring Committee (DMC) and approval given to dose escalate before accrual to the next dosing cohort can begin.

Subjects who discontinue from the study prior to the Study Day 15 assessments for reasons other than a dose-limiting toxicity (DLT), (see definition of Dose-Limiting Toxicity below) will be replaced. Subjects who experience a DLT should continue to complete all protocol assessments and will not be replaced.

The pattern of enrollment outlined in [Table 1](#) (Section 4) will continue until the maximum tolerated dose (MTD) is determined or the highest planned dose level is tested. Six subjects must be treated at a given dose level before the MTD can be declared. The MTD is defined as the highest PDA-002 dose level for which the incidence of DLT is  $\leq 1$  out of 6 subjects. At any dose level, if 2 or more subjects experience a DLT within 14 days of dosing, that cohort will have exceeded the MTD. If a previous dose level was well tolerated and no subjects experienced DLT at that level, an intermediate dose level may be defined by protocol amendment.

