### **Internal Data Monitoring Committee**

An internal DMC will monitor all safety information to ensure subject safety in accordance with a separate charter. The internal DMC will be comprised of members who are not involved in the day-to-day activities of the PDA-002 DFU study team. The internal DMC will recommend whether continued dosing is appropriate, whether dose escalation should proceed, whether modifications to the protocol design are necessary or whether to end dosing and/or further enrollment at either a specific dose level or for the overall study. The internal DMC will make their determinations based on available AE and clinical data. The decisions of the internal DMC will be documented in meeting minutes. The internal DMC will be convened:

- Upon completion of dosing and Day 15 assessments within each dose level cohort to review cumulative safety information and give approval to dose-escalate prior to enrollment commencing in the next higher dose cohort.
- When a study stopping rule is triggered.

The internal DMC chairman will be called if an unexpected, related SAE should occur. During any period of deliberation by the internal DMC, a temporary hold on enrollment and dosing of new subjects will be instituted until the review is completed.

The sponsor will take appropriate action based upon the recommendations of the internal DMC and this will be communicated to the Investigators. The Investigators will be responsible for notifying their Institutional Review Boards (IRBs).

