**Table 1: Dose Escalation Scheme**

Number of Dose-limiting Toxicities	Action Regarding Study Drug
If 0 out of 3 subjects experience a DLT during the first 14 days of follow-up (Day 15) at a given dose level:	Enroll 3 subjects at the next highest dose level (If at the $100 \times 10^6$ cells dose level, 3 additional subjects will be enrolled).
If 1 out of 3 subjects experience a DLT during the first 14 days of follow-up (Day 15) at a given dose level:	Enroll 3 additional subjects at the current dose level
If $\geq 2$ out of 3 subjects experience a DLT at a given dose level:	Enroll 3 subjects at the next lowest dose level a
If 3 additional subjects are enrolled at a given dose level:	
If 1 subject out of 6 subjects experiences a DLT during the first 14 days of follow-up (Day 15) at a given dose level:	Enroll 3 subjects at the next highest dose level (except if at the highest dose level of $100 \times 10^6$ cells).
If $\geq 2$ subjects out of 6 subjects experience a DLT during the first 14 days of follow-up (Day 15) at a given dose level:	Enroll 3 subjects at the next lowest dose level

Abbreviations: DLT = Dose-limiting toxicities; MTD= Maximum tolerated dose.

a If dose level 1 ( $3 \times 10^6$  cells) exceeds the MTD, a PDA-002 dose level of  $1 \times 10^6$  cells will be evaluated.

All subjects in a given dosing-cohort must complete 14 days of follow-up and the data reviewed by an internal Data Monitoring Committee (DMC), as detailed in Section 6.4) and approval given to dose escalate before accrual to the next dosing cohort can begin.

Subjects who discontinue from the study prior to the Study Day 15 assessments for reasons other than a dose-limiting toxicity (DLT) will be replaced. Subjects who experience a DLT should continue to complete all protocol assessments and will not be replaced.

The pattern of enrollment outlined in [Table 1](#) will continue until the MTD is determined or the highest planned dose level is tested. Six subjects must be treated at a given dose level before the MTD can be declared. The MTD is defined as the highest PDA-002 dose level for which the incidence of DLT is  $\leq 1$  out of 6 subjects. At any dose level, if 2 or more subjects experience a DLT within 14 days of dosing, that cohort will have exceeded the MTD. If a previous dose level was well tolerated and no subjects experienced DLT at that level, an intermediate dose level may be defined by protocol amendment.

[figure not shown]

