### **6.4.1. Dose-Limiting Toxicity**

A DLT is defined as a Grade 2 toxicity not resolving within 14 days suspected to be related to the IP or any toxicity  $\geq$  Grade 3 suspected to be related to the IP.

In the event that 2 separate subjects within a dosing cohort experience a DLT, the events will be forwarded to the internal DMC for review and confirmation as to whether or not the MTD has been exceeded. If the MTD is confirmed by the internal DMC, no further IP administration will occur within that dose level or at any higher dose level. An intermediate dose may be defined by protocol amendment.

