#### **6.4.2. Internal Data Monitoring Committee**

An internal DMC will monitor all safety information to ensure subject safety in accordance with a separate charter. The internal DMC will be comprised of members who are not involved in the day-to-day activities of the PDA-002 DFU study team. The internal DMC will recommend whether continued dosing is appropriate, whether dose-escalation can occur, whether modifications to the protocol design are necessary or whether to end dosing and/or further enrollment at either a specific dose level or for the overall study. The internal DMC will make determinations on study continuation and modifications based on available AE and clinical data. The decisions of the internal DMC will be documented in meeting minutes.

The internal DMC will be convened:

- Upon completion of dosing and Study Day 15 assessments within each dose level to review cumulative safety information and give approval to dose escalate prior to enrollment commencing in the next higher dose cohort.
- When a study stopping rule is triggered (see Section 6.4.3).

The internal DMC chairman will be called if an unexpected, related SAE should occur. During any period of deliberation by the internal DMC, a temporary hold on enrollment of new subjects will be instituted until the review is completed.

The sponsor will take appropriate action based upon the internal DMC recommendation and this will be communicated to the Investigators. The Investigators will be responsible for notifying their IRBs. The internal DMC will evaluate on an ongoing basis all available safety data, in particular all serious adverse events (SAEs) and their potential relationship to PDA-002. The internal DMC may recommend modifications to enrollment or to the study design in order to ensure subject safety. Further explanation of the roles and responsibilities of the internal DMC will be spelled out in the internal DMC charter.

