#### **6.4.3. Stopping Rules**

- Identification of 2 or more subjects within a dosing cohort with  $\geq$  Grade 2 allergic reaction that is suspected to be related to the IP.
- Identification of 2 or more subjects within a dosing cohort experiencing an unexpected, treatment-related SAE or DLT within 14 days following the initial dose of the IP.

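### While the DMC reviews two DLTs in a cohort, no stated hold covers the Day 8 dose of a subject already under treatment

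*Protocol*

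**What the plan says.** The criterion is stated in the protocol summary (Study Design), in Protocol 4.1 and in SAP 4.1: "if 2 or more subjects experience a DLT within 14 days of dosing, that cohort will have exceeded the MTD".

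Protocol 6.4.1 says what happens to dosing. After two DLTs in a cohort, "the events will be forwarded to the internal DMC for review and confirmation as to whether or not the MTD has been exceeded". Then: "If the MTD is confirmed by the internal DMC, no further IP administration will occur within that dose level or at any higher dose level".

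For the time of the review there are two versions of a hold:
- Protocol 6.4.2: "a temporary hold on enrollment of new subjects will be instituted until the review is completed".
- Protocol summary, Internal Data Monitoring Committee: "a temporary hold on enrollment and dosing of new subjects will be instituted until the review is completed".

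Protocol 6.4.3 lists as a stopping rule two or more subjects in a cohort "experiencing an unexpected, treatment-related SAE or DLT within 14 days following the initial dose of the IP". It states no action. Under 6.4.2, a triggered rule convenes the DMC, which may recommend "whether to end dosing and/or further enrollment at either a specific dose level or for the overall study".

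New enrollment is settled by Table 1. With two or more DLTs the instruction is "Enroll 3 subjects at the next lowest dose level".

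Every subject is scheduled for doses on Study Days 1 and 8, and first doses are separated by at least 48 hours (Protocol 4.1 and 8.2).

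**The concern.** The stop to dosing waits for a committee decision, and the hold that bridges the wait is worded for new subjects. A subject who has had the first injections but not the second falls between the two. If that subject has had no adverse event, none of the reasons for stopping treatment listed in 8.2.1 plainly applies, because none is a cohort-level safety reason.

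At stake is a second dose of a cell product, in the first trial of its intramuscular use, at a level where the 4.1 criterion has already been met. A held dose can usually be given later; an injected one cannot be withdrawn.

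**Working it through.** **1. Does any text suspend a pending Day 8 dose?**

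| Place | What it governs | Covers a pending Day 8 dose? |
|---|---|---|
| Protocol 4.1, summary, SAP 4.1 | Criterion for exceeding the MTD | No dosing instruction |
| Table 1 | Next subjects to enroll | No |
| 6.4.1 | All product at that level and above | Yes, but only after DMC confirmation |
| 6.4.2 | Enrollment of new subjects during review | No |
| Summary, DMC section | Enrollment and dosing of new subjects | No, on its natural reading |
| 6.4.3 | Triggers only | No action stated |
| 8.2.1 | Reasons for stopping one subject | No cohort-level reason |

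The only figure in the plan that bears on this is the cap of 24 subjects, which is 4 cohorts × 6. The rest is a timing check on stated assumptions.

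**2. Calendar at the fastest stagger.** Starts on days 1, 3 and 5 give second doses on days 8, 10 and 12. If subjects 1 and 2 have Grade 3 or higher DLTs and the second is known on days 5 to 11, subject 3 has started and the day 12 dose is pending. Before day 5, subject 3 has not started and the existing hold applies.

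**3. How many subjects.** Two DLTs in the first three leave one DLT-free subject. After 1 of 3, the first DLT among the three added subjects is the second at that level and leaves up to two. At the top level after 0 of 3, two DLTs in the added group leave one. The added group starts only after the first three finish 14 days, when their own second doses are past. The maximum is 2.

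**4. Grade 2 DLTs.** These need 14 days without resolution, so a Day 1 event is established on day 15. With starts s days apart, subject 3's second dose falls on day 8 + 2s.
- Grade 2 in subject 1, Grade 3 or higher in subject 2: 8 + 2s > 15, so s ≥ 4 whole days.
- Grade 2 in both: 8 + 2s > 15 + s, so s ≥ 8.

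**5. Chance of two or more DLTs at some level**, with a flat per-subject rate p (assumed; the plan gives none). At a lower level: P(≥2 of 3) + P(1 of 3) × P(≥1 of 3). At the top level: P(≥2 of 6). For p = 10%:
- lower: 0.028 + 0.243 × 0.271 = 0.0939
- top: 1 − 0.5314 − 0.3543 = 0.1143
- some level: 1 − 0.9061³ × 0.8857 = 0.341

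The same formula gives 2%, 11%, 34%, 58%, 77% and 89% at p = 2%, 5%, 10%, 15%, 20% and 25%.

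**6. Chance that at least one started, DLT-free subject has the Day 8 dose pending, given two or more DLTs at a level.** This was simulated with 200,000 runs per setting. Assumptions: Grade 3 or higher DLTs recognised at onset; p = 10% and 25%; lower and top level; added group starting 14 days after the third start. Onset is uniform over 14 days, within 24 hours of either dose, or uniform over the first 7 days.

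| Days between starts | Review of 7 days or more | Review of 3 days |
|---|---|---|
| 2 | 44% to 76% | 29% to 44% |
| 4 | 44% to 57% | 20% to 29% |
| 7 | 0% to 30% | 0% to 13% |
| 14 | 0% | 0% |

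**7. Joint size (step 5 × step 6, review of 7 days or more).**
- p = 10%, starts 2 days apart: 0.341 × 0.437 = 0.15 to 0.341 × 0.758 = 0.26.
- p = 10%, starts 7 days apart: at most 0.341 × 0.295 = 0.10.
- p = 5%, starts 7 days apart: at most 0.108 × 0.295 = 0.03, borrowing the conditional range from the higher rates.

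**8. Recognition lag.** Only serious events have a 24-hour reporting deadline. With an assumed 3-day lag, and counting only subjects who started before the second DLT began, the 2-day figure falls to roughly a quarter to a half, and the 4-day figure to between a fifth and 30%. The lag also lets further subjects start. With starts on days 1, 15 and 29, a DLT in subject 2 that begins on day 28 and is recognised on day 31 leaves subject 3's dose pending on day 36. The zero at 14 days therefore rests on prompt recognition of Grade 3 or higher events. Two Grade 2 DLTs would also leave that dose pending (established on day 15 + 14 = 29, dose due on day 36).

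**The case against.** The case for leaving the text alone has real substance.

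- **DMC confirmation is a legitimate choice.** A DLT turns on grade and suspected relationship, and having a committee confirm both before declaring a level too toxic is reasonable. This stands, and the point is not directed at that step.
- **Sections 4.1 and 6.4.1 need not conflict.** A reader might infer that sites following one would act differently from sites following the other. The documents do not support that. Section 4.1 gives no instruction about dosing subjects already started, so there is nothing in it for a site to follow differently. Cohorts are spread over about 14 centers, and the sponsor passes DMC outcomes to investigators.
- **The heading of 6.4.3 implies a stop.** That is its ordinary sense, but the section states no action, and 6.4.2 attaches only the convening of the DMC.
- **Nothing obliges anyone to give the dose.** The reasons in 8.2.1 are described as sufficient, not exclusive, and the DMC can recommend ending dosing. This stands: the text permits the dose, and does not require it.
- **The charter may contain a hold.** Both documents place DMC operating detail there, and it was not available. A hold found only in the charter would still be missing from the text that investigators work from.
- **The highest percentages need fast accrual and prompt recognition.** The 48-hour rule is a minimum interval, not an accrual forecast. Protocol 4.2 also expects all dose levels to be well tolerated.
- **The phrase about the MTD being confirmed is a slip.** The sentence before it leaves only one sensible meaning. It is still worth correcting.

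**Conclusion.** The gap is real and narrow. Between the second DLT and the DMC's decision, the supplied text does not suspend the Day 8 dose of a DLT-free subject already started, although the level meets the 4.1 criterion for exceeding the MTD. New enrollment is not affected.

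At most 1 or 2 subjects per level are exposed. The exposure is greatest when starts are a few days apart and DLTs are recognised quickly. Under the simulation's assumptions it vanishes at 14-day spacing, and it is small overall if DLT rates are low. The percentages rest on assumed DLT rates, onset patterns, spacing and review length. None of them is a chance that the DMC disagrees or that the MTD is wrong.

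A reader might also infer that the declared MTD is at risk. It is not: the SAP derives DLTs under its own rules in 11.1, and no analysis depends on this wording. It is a cheap improvement to a safety rule.

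**What to change.** - In 6.4.1, 6.4.2 and the protocol summary, state that from the second DLT in a cohort, or from any 6.4.3 trigger, all product administration at that level and above is held until the DMC decides, including pending Day 8 doses. Use the same hold wording in 6.4.2 and the summary.
- Keep the DMC confirmation step.
- In 6.4.1, reword the condition for the permanent stop so that it reads: if the DMC confirms that the MTD has been exceeded.
- State whether a subject whose second dose was delayed or missed under the hold still counts toward the 3 or 6 subjects at that level or is replaced. The current replacement rule covers only subjects who leave the study before the Day 15 assessments.

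The cost is a few sentences in the protocol and no change to any SAP analysis. The downside is a delayed or missed second dose for 1 or 2 subjects if the DMC clears the events. The SAP 9.2 compliance listing already provides for interrupted or discontinued injections.

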#### **6.4.2. Internal Data Monitoring Committee**

An internal DMC will monitor all safety information to ensure subject safety in accordance with a separate charter. The internal DMC will be comprised of members who are not involved in the day-to-day activities of the PDA-002 DFU study team. The internal DMC will recommend whether continued dosing is appropriate, whether dose-escalation can occur, whether modifications to the protocol design are necessary or whether to end dosing and/or further enrollment at either a specific dose level or for the overall study. The internal DMC will make determinations on study continuation and modifications based on available AE and clinical data. The decisions of the internal DMC will be documented in meeting minutes.

The internal DMC will be convened:

- Upon completion of dosing and Study Day 15 assessments within each dose level to review cumulative safety information and give approval to dose escalate prior to enrollment commencing in the next higher dose cohort.
- When a study stopping rule is triggered (see Section 6.4.3).

The internal DMC chairman will be called if an unexpected, related SAE should occur. During any period of deliberation by the internal DMC, a temporary hold on enrollment of new subjects will be instituted until the review is completed.

The sponsor will take appropriate action based upon the internal DMC recommendation and this will be communicated to the Investigators. The Investigators will be responsible for notifying their IRBs. The internal DMC will evaluate on an ongoing basis all available safety data, in particular all serious adverse events (SAEs) and their potential relationship to PDA-002. The internal DMC may recommend modifications to enrollment or to the study design in order to ensure subject safety. Further explanation of the roles and responsibilities of the internal DMC will be spelled out in the internal DMC charter.

#### **6.4.3. Stopping Rules**

- Identification of 2 or more subjects within a dosing cohort with  $\geq$  Grade 2 allergic reaction that is suspected to be related to the IP.
- Identification of 2 or more subjects within a dosing cohort experiencing an unexpected, treatment-related SAE or DLT within 14 days following the initial dose of the IP.

#### **6.4.4. Injection-Related Reactions**

An injection-related reaction is any sign or symptom experienced by a subject during the injections or any event occurring within 24 hours of the IP administration. The duration and severity of injection-related reactions will be collected and recorded on the eCRF.

Any allergic reaction  $\geq$  Grade 3 and associated with the IP is to be reported as a SAE.

#### **6.4.5. Other Safety Assessments**

##### **Adverse Events and Concomitant Medications**

Adverse events and concomitant medication use will be collected from the time of the signing of the informed consent until Month 24.

##### **Physical Examination**

A routine physical examination will be performed at all visits. Routine physical examination to include vital signs and examination of skin, head, eyes, nose, throat, neck, joints, lungs, heart, abdomen (including liver and spleen), lymph nodes, extremities, and neurological function particularly sensory and motor function of the affected leg.

**All abnormal findings at baseline will be recorded as medical history. Any physical examination finding that is judged by the Investigator as a clinically significant change (worsening) compared to a baseline value will be considered an AE and should be recorded and monitored as such.**

##### **Vital Signs**

Vital sign measurements include:

- Temperature (°C)
- Pulse (beat/minute)
- Pulse oximetry (%) only on Study Days 1 and 8
- Respiration (breaths/minute)
- Resting systolic and diastolic blood pressure (mmHg)
- Height (cm) (At Screening only or when possible)
- Weight (kg)

Before pulse and blood pressure are measured, the subject must be resting for at least 5 minutes (the same position and arm should be used each time vital signs are measured for a given subject).

On the day of IP administration, vital signs (including heart rate, respiration, blood pressure, body temperature, and pulse oximetry) will be monitored prior to starting the injections and every 15 minutes for a minimum of 2 hours after completion of the injections.

Any clinically significant finding during Screening will be recorded as medical history. Any vital sign value that is judged by the Investigator as a clinically significant change (worsening) compared to a baseline value will be considered an AE and be recorded and monitored as such.

## **Contraception**

Females of child bearing potential (FCBP)\* must use adequate contraception for the duration of their participation in the study including all Follow-Up Periods (up to 24 months postdose). Adequate contraception is defined as the simultaneous use of two of the following forms of contraception methods: oral, injectable or implantable hormonal contraception; tubal ligation; intrauterine device (IUD); barrier contraceptive with spermicide; or a vasectomized partner.

Males (including those who have had a vasectomy) must agree to use barrier contraception (latex condoms) when engaging in sexual activity with FCBP for the duration of the study and the Follow-Up Period (up to 24 months postdose).

